15.4.2 Incomplete Stop Date

When required per the protocol, follow the same rules as in 15.3.2.

15.4.3 Incomplete Start/Stop Time

There is no imputation for missing start/stop time for AEs. In such cases, only the date part will be used to compare with the dosing date. If an AE start date is before the first dose of MDTP, it will be summarized in the SDTP outputs; if an AE start date is on or after the first dose of MDTP, it will be summarized in the MDTP outputs.

15.5 Missing Severity Assessment for Adverse Events

If severity is missing for an AE starting prior to the date of the first dose of investigational product, then a severity of “Mild” will be assigned. If the severity is missing for an AE starting on or after the date of the first dose of investigational product, then a severity of “Severe” will be assigned. The imputed values for severity assessment will be used for incidence summaries, while the actual values will be used in data listings.

15.6 Missing Relationship to Investigation Product for Adverse Events

If the relationship to investigational product is missing for an AE starting on or after the date of the first dose of investigational product, a causality of “Related” will be assigned. The imputed values for relationship to double-blind investigational product will be used for incidence summaries, while the actual values will be presented in data listings.

15.7 Character Values of Clinical Laboratory Variables

If the reported value of a clinical laboratory variable cannot be used in a statistical analysis due to, for example, that a character string is reported for a numerical variable. The appropriately determined coded value will be used in the statistical analysis. The following rules will be followed to determine the coded value: if the reported values contain character strings of “<” or “≤”, then coded value will be half of the original values. For example, if reported value is <5 then coded value will be 2.5. If the reported value contain character strings of “>” or “≥”, then coded value will be twice of the original values. For example, if reported value is >5 then coded value will be 10. However, the actual values as reported in the database will be presented in data listings.

Table 9 Examples for Coding of Special Character Values for Clinical Laboratory Variables

Clinical Laboratory Test	Possible Results (in SI units)	Coded Value for Analysis
Chemistry: ALT	< 5	2.5
Chemistry: AST	< 5	2.5
Chemistry: Total Bilirubin	< 2	1
Urinalysis: Glucose	≥ 55	110
	≤ 0	0
Urinalysis: pH	> 8.0	16

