AST/SGOT	NA	> 3 × ULN
ALP	NA	> 3 × ULN
Total bilirubin	NA	> 1.5 × ULN
Sodium	< 0.9 × LLN	> 1.1 × ULN
Potassium	< 0.85 × LLN	> 1.2 × ULN
Creatinine	NA	> 1.5 × ULN
BUN	NA	> 3 × ULN
Bicarbonate	< 0.5 × LLN	> 1.3 × ULN
Glucose	0.6 × LLN	> 3.5 × ULN
Calcium	< 0.7 × LLN	> 1.3 × ULN
Phosphorus	< 0.3229 mmol/L	> 1.6145 mmol/L
Chloride	< 0.8 × LLN	> 1.2 × ULN
URINALYSIS		
pH	< 4.5	> 7.2

Specific Gravity	< 0.9 × LLN	> 1.1 × ULN
Blood		> 5
WBC		> 5
Glucose		≥ 100 mg/dL
Protein		> 20 mg/dL
Bilirubine		Other than negative
Nitrite		Other than negative
Ketones		Other than negative
Leukocyte esterase		Small, moderate and large (eg other than negative OR trace)

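### The laboratory recoding rule gives an impossible urine pH of 16 for analysis, and the specific-gravity PCI limits cannot flag any real measured value

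*SAP*

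**What the plan says.** SAP 15.7 covers laboratory results that arrive as character strings where a number is expected. For '<' or '≤', "then coded value will be half of the original values"; for '>' or '≥', "then coded value will be twice of the original values". The rule is general, with no exception for bounded scales. Table 9 works it through, including the row "Urinalysis: pH > 8.0 16". On use, 15.7 states: "The appropriately determined coded value will be used in the statistical analysis". Listings are exempt: "the actual values as reported in the database will be presented in data listings".

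SAP 11.2 plans descriptive statistics and change from baseline for quantitative laboratory variables, and its variable list includes urine pH and specific gravity. A result is PCI if it meets either the low or the high limit in Table 6. For urine pH the limits are < 4.5 and > 7.2. For "Specific Gravity" they are < 0.9 × LLN and > 1.1 × ULN. The reference ranges are not printed; Protocol 7.2.2.6 leaves them to the laboratory. SAP Section 16 plans urinalysis PCI tables for both treatment periods (14.3.4.2.5 and 14.3.4.2.6) and marks the multiple-dose one for the interim.

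**The concern.** Doubling or halving a censoring limit may be tolerable for a concentration that can range over multiples of that limit. It fails on a scale with a narrow physical range, such as pH or specific gravity, where it gives numbers that cannot occur. Cohorts have 5 active subjects (SAP 2.3), so a single recoded value can dominate a mean.

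Multipliers of LLN and ULN fail for specific gravity for a related reason. The whole range of real values lies close to 1, so a 10% margin puts both limits outside anything a urine sample can show. A criterion that cannot be met reports zero events whatever the data. Safety is the primary objective, so a planned safety table should not contain a row that is empty by construction or filled only by coding artefacts.

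**Working it through.** **Inputs from the documents.** Coding factors 2 and 0.5, and the Table 9 examples (SAP 15.7). PCI limits (SAP Table 6). Five active subjects per cohort (SAP 2.3).

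**Inputs assumed.** LLN 1.000–1.010 and ULN 1.020–1.040 for specific gravity; real urine values 1.000–1.060; possible reporting cut-offs as stated below.

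**1. Reproduce Table 9.** 5/2 = 2.5 (ALT and AST); 2/2 = 1 (bilirubin); 2 × 55 = 110 and 0/2 = 0 (glucose); 2 × 8.0 = 16 (pH). All six codings match the SAP. The value 16 lies outside the 0–14 pH scale.

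**2. Effect on a mean pH.** Shift = (16 − true value)/5. The true value is above 8.0, so the shift is at most (16 − 8.0)/5 = 1.6 units. The entire non-PCI band in Table 6 is 7.2 − 4.5 = 2.7 units wide.

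**3. PCI flags from the Table 9 examples.**
- pH '> 8.0': any such value exceeds 7.2, so the flag is correct before and after coding.
- ALT, AST and bilirubin with '<': Table 6 has no low limit, so there is no flag.
- Glucose '≥ 55': the Table 9 column is headed SI units. Read as mmol/L, 55 is about 991 mg/dL, above the 100 mg/dL limit, so the flag is true. It would be false only if the 55 were in mg/dL.

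Read in SI units, no Table 9 row gives a false flag. Other pH cut-offs could: an assumed '< 5.0' becomes 2.5, below 4.5, although a true value from 4.5 up to 5.0 is not PCI.

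**4. Specific-gravity limits for measured values.**

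| Limit | Formula | Over the assumed range | Needed to reach real values |
|---|---|---|---|
| Low | 0.9 × LLN | 0.900–0.909 | LLN of at least 1.000/0.9 = 1.111 to reach water |
| High | 1.1 × ULN | 1.122–1.144 | ULN of at most 1.060/1.1 = 0.964 to reach 1.060 |

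Neither condition is plausible, so the criterion flags no real measured value anywhere in the assumed range.

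**5. Specific gravity if reported as censored (hypothetical).** '> 1.030' becomes 2.06, and cut-offs of 1.025–1.050 give 2.05–2.10, all above 1.144. '< 1.005' becomes about 0.50, and cut-offs of 1.000–1.010 give 0.500–0.505, all below 0.900. Every such result would be flagged, although the reported limit itself meets neither criterion.

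**The case against.** The strongest reply is that little of this need reach a reader. Section 16 titles the by-visit urinalysis tables (14.3.4.1.5 and 14.3.4.1.6) as qualitative, whereas the hematology and biochemistry tables are titled quantitative, so a mean pH may never be produced. Listings keep the reported result, and a listing of PCI subjects (16.2.8.1.3) is planned, so a '>' sign would be visible. Investigators judge the clinical significance of out-of-range results (Protocol 7.2.2.6), and no stopping criterion in Protocol 4.5.4 uses urinalysis PCI counts. All of this stands and limits the impact. It does not make 16 a usable analysis value. SAP 11.2 lists pH and specific gravity without excluding them from summary statistics, and the urinalysis PCI tables are planned in any case.

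Two stronger readings are tempting and are not supported:

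- A reader might infer that the pH example itself creates a false PCI flag. It does not, because anything above 8.0 is PCI under the 7.2 limit.
- A reader might infer that ordinary dilute or concentrated urine will be falsely flagged. That requires the laboratory to report specific gravity with an inequality sign. Table 9 has no such row and nothing else in the documents shows it, so 2.06 and 0.50 are illustrations and their frequency cannot be estimated.

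**Conclusion.** The point holds as two separate, minor defects in stated rules.

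First, SAP 15.7 prints an impossible analysis value for urine pH. Its effect on a 5-subject mean is at most 1.6 units for one such result, and arises only if a mean or change from baseline is produced.

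Second, the specific-gravity PCI criterion is inert for measured values. This rests on an assumed reference range, but the conclusion is the same across LLN 1.000–1.010 and ULN 1.020–1.040. False specific-gravity flags are possible but conditional on censored reporting. Nothing here bears on dose-escalation stopping rules. The matter is worth correcting because the affected tables are planned and the correction is easy.

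**What to change.** - **SAP 15.7 and Table 9:** code censored results for pH and specific gravity at the reporting limit, so that pH '> 8.0' becomes 8.0.
- **PCI status:** determine it from the reported result, treating '>' or '<' as beyond the reporting limit, and not from the coded number. This matters because coding '> 1.030' as 1.030 and then testing for values strictly above a ULN of 1.030 would miss a result known to be out of range. The same holds for '< 1.005' against an LLN of 1.005.
- **SAP Table 6:** replace the specific-gravity multipliers with limits that real values can reach, such as outside the laboratory reference range, or drop the criterion. Changing 15.7 alone would leave it inert.

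The cost is SAP wording and minor programming, with no new data. Reference-range limits would flag more mildly out-of-range specific gravities. The multiple-dose urinalysis PCI table is marked for the interim, and SAP 13 reports the June 2018 interim as already conducted, so a short note should explain any difference from outputs already issued.

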15.8 Time Ranges for Analysis of Time Points

Subjects do not always adhere strictly to the visit schedule timing in the protocol. Mutually exclusive relative visit and time windows are defined below to provide the derived visits and time points that correspond to scheduled visits and time points. Assessments will be mapped to the corresponding visits and time points based on the visit and time window. Designation of visits and time points for assessments is tabulated below. If more than one assessment falls into a given visit and time window, the assessment closest to the planned visit and time will be used for analysis. If both assessments are equal distant from the planned assessment visit and timepoint, the earlier assessment will be used for analysis.

Table 10 Visit and Time Ranges for Assessment at Every Schedule Visit and Time Point

Protocol Scheduled Visits	Visit Windows (Days)
Screening	≥ -42 - ≤ -3
Day -2	-2
Day -1	-1
Day 1	1
Day 2	2
Day 7	≥ 3 - ≤ 10
Day 14	≥ 11 - ≤ 17
Day 21	≥ 18 - ≤ 25
Day 26	26
Day 27	27
Day 28	28

Day 29	29
Follow-up	> 29

For SDTP non-dosing days including Day -2, Day -1 and Day 2, the derived timepoints will be the same as the scheduled timepoints. For MDTP non-dosing days including Day -2, Day -1 and Day 29, the derived timepoints will also be the same as the scheduled time points. For both SDTP and MDTP dosing days, designation of timepoints for post-dosing assessments is tabulated below.

Protocol Scheduled Timepoints	Time Windows
Predose	Predose
0 m	> 0 m - ≤ 15 m
30 m	> 15 m - ≤ 45 m
1 h	> 45 m - ≤ 90 m
2 h	> 90 m - ≤ 150 m
3 h	> 150 m - ≤ 210 m
4 h	> 210 m - ≤ 300 m
6 h	> 300 m - ≤ 420 m
8 h	> 420 m - ≤ 600 m
12 h	> 600 m - ≤ 1440 m

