Gonioscopy to assess the iridocorneal angles will be performed at screening and on Day 29. Gonioscopy should be performed after the corneal epithelium has been evaluated for defects with fluorescein and after IOP has been measured but before dilated posterior segment examination (Day 29). The angle of each eye should be graded in all 4 quadrants using the Shaffer grading system.

Noncontact Specular Microscopy

Noncontact specular microscopy will be performed to assess endothelial cell count at the following visits:

- Screening
- SDTP (Cohort A only): Day -1 and Day 2
- MDTP (all cohorts): Day -1 and Days 14 and 29

Details of the procedure will be found in the ophthalmology procedures manual.

Corneal Pachymetry

Corneal pachymetry to assess central corneal thickness will be performed after the predose examination and at 1, 2, 4, and 12 hours after dosing. With the pachymeter set to perform a single measurement, take and record 3 consecutive measurements at each applicable time point at the following visits:

- Screening
- SDTP (Cohort A only): Day -1 and Days 1 and 2
- MDTP (all cohorts): Day -1 and Days 1, 2, 7, 14, and 29

If the range of the measurements is 15 microns or less, the set of readings is acceptable; if not, discard all measurements and repeat until an acceptable set of 3 measurements is obtained. Record all 3 measures in the source document and the eCRF.

See [Table 2](#), [Table 3](#), [Table 4](#), and [Table 5](#) for detailed timings by cohort.

Full details of the procedure are provided in the ophthalmology procedures manual.

Drop Comfort Assessment

Drop comfort assessment should be performed immediately after instillation of investigational product and before IOP assessment (which requires topical anesthetic).

Drop comfort assessments will be performed for the first dose of the day as follows:

- SDTP (Cohort A only): Day 1
- MDTP (all cohorts): Days 1, 7, 14, 21, 27, and 28

Drop comfort assessment will not be captured in the subject's daily journal.

The drop comfort assessment will be performed for each eye except for Cohort A during the SDTP, when only the study eye will be assessed. The assessment will be performed immediately and 1, 2, and 3 minutes after instillation of the investigational product. The subject will be asked to rate drop comfort on a scale of 0-10, where 0=very comfortable and 10=very uncomfortable.

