11.6 Other Safety Variables

11.6.1 Drop comfort assessment

Drop comfort assessment should be performed immediately after instillation of investigational product and before IOP assessment (which requires topical anesthetic). Drop comfort assessment

will be measured at the visits specified in Table 1; the time points during each visit are specified in Table 2, Table 3, Table 4, and Table 5 for Cohorts A, B, C, and D, respectively.

The drop comfort assessment will be performed for each eye (study eye, non-study eye, and either eye) except for Cohort A during the SDTP, when only the study eye will be assessed. For either eye summaries, the assessment denoting the most discomfort (e.g., greater value) will be summarized. The assessment will be performed immediately and 1, 2, and 3 minutes after instillation of the investigational product. The subject will be asked to rate drop comfort on a scale of 0-10, where 0=very comfortable and 10=very uncomfortable.

If the score is not ≤ 3 at minute 3, the drop comfort assessment should be repeated at 5, 10, and 15 minutes after dosing until the score is ≤ 3 . If the score is >3 at 15 minutes after dosing, it should be recorded as an AE.

Descriptive statistics for drop comfort scores at each assessment time point during the SDTP will be presented for study eye by treatment group. Descriptive statistics for drop comfort scores at each assessment time point during the MDTP will be presented by eye (study eye, non-study eye, either eye) and by treatment group. The score of drop comfort at each assessment visit and time point will be listed by individual subject.

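### SAP 15.8 and SAP 11.6.1 conflict on drop comfort: the time-window rule would put one score per eye and dose into summary tables meant to show every scored minute

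*SAP*

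**What the plan says.** **Collection.** SAP 11.6.1 sets the times: "The assessment will be performed immediately and 1, 2, and 3 minutes after instillation of the investigational product". If the score is still above 3 at minute 3, "the drop comfort assessment should be repeated at 5, 10, and 15 minutes after dosing", stopping once it is 3 or lower. Protocol 7.2.2.3 gives the multiple-dose days as "MDTP (all cohorts): Days 1, 7, 14, 21, 27, and 28", for the first dose of the day and each eye. Cohort A adds Day 1 of the single-dose period, study eye only.

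**Summary.** For the multiple-dose period SAP 11.6.1 states: "Descriptive statistics for drop comfort scores at each assessment time point during the MDTP will be presented by eye". It asks for the same in the study eye for the single-dose period. It also lists every score by subject.

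**Windows.** SAP 15.8 is a general convention: "Assessments will be mapped to the corresponding visits and time points based on the visit and time window". On scope it says: "For both SDTP and MDTP dosing days, designation of timepoints for post-dosing assessments is tabulated below". The time-point table there (part of SAP Table 10) has one entry between predose and 30 m, namely 0 m, running from more than 0 up to and including 15 minutes. The 30 m window begins after 15 minutes. Where a window holds several assessments, "the assessment closest to the planned visit and time will be used for analysis"; a tie goes to the earlier one. No assessment is exempted by name.

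**The concern.** Every drop comfort score is scheduled within the first 15 minutes, so all of them fall in the one 0 m window, and the rule lets one through to the analysis. SAP 11.6.1 cannot then be carried out, because no derived time point exists at 1, 2, 3, 5, 10 or 15 minutes.

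Safety and tolerability form the primary objective, and drop comfort is one of the measures named for it (Protocol 9.9.1, SAP 11). Protocol 1.3 names local ocular discomfort as the anticipated toxicity and ties escalation of dosing frequency to tolerability. Scores are repeated in order to see whether discomfort fades within a few minutes or persists. A table holding one score per dose cannot show that.

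**Working it through.** The documents give no figure on this point, so there is nothing to reproduce. The check applies the SAP 15.8 windows to the scheduled times.

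**Inputs**
- Windows (SAP 15.8): 0 m is >0 to ≤15 min; 30 m is >15 to ≤45 min; one record kept per window, the closest to the planned time.
- Mandatory times (SAP 11.6.1): immediate, 1, 2 and 3 min, so k = 4 scores.
- Repeats (SAP 11.6.1): 5, 10 and 15 min, stopping at a score of 3 or lower, so k is at most 7. All three repeats are needed only if the score is still above 3 at 10 minutes.
- Assessed doses (Protocol 7.2.2.3): 6 multiple-dose days × 2 eyes = 12 eye-doses. Cohort A has one more from the single-dose period, giving 13.
- Assumption: the one-record rule runs separately for each eye. SAP 15.8 does not say so.

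**Per eye and dose.** With all k scores in one window and 1 kept, the share not summarised is (k − 1)/k.

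| Scores taken (k) | Kept | Not summarised |
|---|---|---|
| 4 (no repeat) | 1 | 3/4 = 75% |
| 5 | 1 | 4/5 = 80% |
| 6 | 1 | 5/6 = 83% |
| 7 (all repeats) | 1 | 6/7 = 86% |

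**Per completing subject**
- Cohorts B–D: 12 kept of 12 × 4 = 48 at the minimum schedule; 12 of 12 × 7 = 84 if every dose needed all repeats.
- Cohort A: 13 kept of 13 × 4 = 52, or 13 of 13 × 7 = 91.
- If 11.6.1 governs instead, all 48 (or 52) mandatory scores are summarised and nothing is lost.

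**Edge cases**
- An immediate score with a recorded time just after dosing is the one kept. If its recorded time equals the dosing time, elapsed time is 0 and it meets no post-dose window. The 1-minute score is then kept under the 0 m label. The count is unchanged, but the retained value is a different one.
- A last repeat recorded slightly after 15 minutes moves to the 30 m window. Two of 7 are then kept and 5/7 = 71% are not summarised.

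**Is the 0 m row meant for something else?** Among assessments whose post-dose times can be read in the SAP text, PK and IOP start at 30 minutes, visual acuity, conjunctival redness and pachymetry at 1 hour, and fluorescein staining at 2 hours. Drop comfort is the only one of these taken in the first 15 minutes. Some rows of the detailed schedules are not legible, so this comparison is not exhaustive.

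**The case against.** The strongest reply is that the specific section should govern. SAP 11.6.1 names the minutes and orders statistics at each. SAP 15.8 exists to handle departures from schedule, not to merge times that are themselves scheduled. A programmer would have to override 11.6.1 to lose the scores. Scores may also be captured by nominal minute, in which case elapsed-time windows might never be applied to them; the case report form is not shown, and SAP Section 1 places the table specifications in a separate document.

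Much of this stands. A reader might infer that the plan intends to throw away most drop comfort data. The documents do not support that: 11.6.1 shows the opposite intent, and the by-subject listing (16.2.6.1) holds every score, which counts for something in a descriptive study with 5 active and 2 placebo subjects per cohort. A reader might also infer that the 15-minute scores above 3 that define an adverse event would vanish. They would not: SAP 11.6.1 has such a score recorded as an adverse event, which reaches the treatment-emergent tables whatever 15.8 does.

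The reply does not remove the conflict. The wording of 15.8 covers post-dose assessments on dosing days without exception, and nothing in the SAP ranks the two sections. The drop comfort tables (14.3.7.1.1 and 14.3.7.1.2) are marked as non-standard for the sponsor, so the output list points to no standard layout that would settle it. Intent can be inferred, but a stated rule still gives the wrong result if followed.

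**Conclusion.** The point holds as an unreconciled conflict between two SAP sections. Followed literally and per eye, 15.8 leaves 1 of 4 mandatory scores per assessed dose in the summary tables, and 1 of up to 7 with repeats: a loss of 75% to 86%, or 71% where the last repeat slips past 15 minutes. If 11.6.1 prevails, the loss is zero.

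The effect is limited to the summary tables; listings and adverse event reporting are unaffected. It would be going too far to call drop comfort the main tolerability measure, because the documents list it among several without ranking them. The gap at exactly 0 minutes is minor, since it matters only when the recorded score time equals the dosing time. This is a low-severity point, worth correcting because it touches a named measure of the primary objective.

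**What to change.** Add a sentence to SAP 15.8: drop comfort is exempt from the time windows and is summarised by nominal minute (immediate, 1, 2 and 3, and 5, 10 and 15 where repeated), as 11.6.1 requires. Nominal minutes also deal with a last repeat taken just after 15 minutes.

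As a minor edit, start the 0 m window at ≥ 0 m, so that a record made after instillation but carrying the same clock time as dosing is not left unassigned.

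The cost is one sentence and one symbol in the SAP, plus a check that the specifications for the two drop comfort tables have minute-level rows. No new data are needed.
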